3.4.2. RSV Signs and Symptoms

RSV associated signs and symptoms will be assessed (as present/not present) by HCP (Appendix 10A of Protocol). The pre-dose assessment on Day 1 will be considered the baseline. Further assessments will be made over time with hospitalized patients assessed daily. Each sign and symptom will be analyzed separately.

Durations of RSV signs and symptoms at baseline will be determined. Duration at baseline is calculated as: baseline date – onset date + 1.

3.4.3. CCI

CCI

3.5. Baseline Variables

Baseline values will be the last value recorded prior to starting study treatment unless otherwise specified.

4. ANALYSIS SETS (POPULATIONS FOR ANALYSIS)

Data for all participants will be assessed to determine if participants meet the criteria for inclusion in each analysis population prior to unblinding and releasing the database and classifications will be documented per standard operating procedures.

Participant Analysis Set	Description
Enrolled	"Enrolled" means a participant's, or their parent(s)/legal guardian's, agreement to participate in a clinical study following completion of the informed consent process and randomization.
Full analysis set	All participants randomly assigned to study intervention and who take at least 1 dose of study intervention.

PFIZER CONFIDENTIAL

DMB02-GSOP-RF02 8.0 Statistical Analysis Plan Template

TMF Doc ID: 98.03

Page 10 of 20

Safety analysis set	All participants randomly assigned to study intervention and who take at least 1 dose of study intervention. Participants will be analyzed according to the product (sisunatovir / placebo) they actually received.
PK Concentration Population	All participants randomly assigned to study intervention and who take at least 1 dose of study intervention and in whom at least 1 concentration value can be reported.
PK Parameter Analysis Population	All participants randomly assigned to study intervention and who take at least 1 dose of study intervention and in whom at least 1 of the PK parameters of interest can be reported
Biomarker Analysis Population	All participants randomly assigned to study intervention and who take at least 1 dose of study intervention and in whom at least 1 of the measured parameters of interest can be reported.

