Participants may be replaced at Sponsor discretion for the following reasons: if the participant's parent(s)/legal guardian withdraws consent, if the participant misses any dose before providing the **CCI** sample on Day **CCI** or **CCI** if the participant misses any PK samples, if IMP is discontinued, or if the participant's RSV test results at screening are not confirmed by the central laboratory RSV test result, if participant was exposed to a prohibited concomitant medication or if Day 1 RSV RNA level by RT-qPCR is less than the lower limit of quantification.

Participant(s) with discrepant central laboratory RSV test result will not be included in the primary analysis.

For each participant, the study will have a maximum duration of approximately 5 weeks. This includes a screening period of 1-2 days, a **CCI** day Treatment period and a **CCI** follow-up period **CCI**. The highest, well-tolerated dose will be determined for the corresponding age band in this study.

Approximately a maximum of 108 participants **CCI** in each cohort + **CCI** additional in each cohort if necessary) will be enrolled. The minimum number of participants (based on a minimum of **CCI** participants per Cohort) is approximately **CCI** evaluable participants as Cohorts 2 (2A, 2B, 2C) and 3 (3E, 3F, 3B, 3D) are optional in the study.

The study will be conducted as a double-blind, sponsor-open study and will be conducted globally with the number of study sites yet to be determined. No study intervention will be provided to participants at the end of their study participation (Section 6.7).

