2.2. Study Objectives, Endpoints, and Estimands

Type	Objective	Endpoint
	Primary:	Primary:
Safety (Section 6.1)	To evaluate the safety and tolerability of sisunatovir compared to placebo in participants with RSV-LRTI.	
 Incidence of TEAEs. Incidence of AEs and SAEs leading to discontinuations. Incidence of clinically significant abnormal laboratory values and vital signs.
	Secondary:	Secondary:
PK (Section 6.2.1)	To characterize the PK of sisunatovir in participants with RSV-LRTI.	
 Plasma concentrations of sisunatovir at steady state (Day [REDACTED] or later).
	Tertiary:	Tertiary:
Other - Virological response (Section 6.4.1)	To describe the viral load in Nasopharyngeal (NP) samples over time in participants with RSV-LRTI.	
 Viral load measured via RT-qPCR in NP swabs over time (including but not limited to change from baseline at each sampled visit and proportion of participants with BLOQ at Day [REDACTED] CCI).
Efficacy (Section 6.4.2)	To describe signs and symptoms assessed by HCP over time in participants with RSV-LRTI	
Signs and symptoms over time (including but not limited to change from baseline at Day [REDACTED] CCI and proportion of participants with each sign at Day [REDACTED] CCI).
 
 CCI [REDACTED]
Other - Virological response (Section 6.4.3)	CCI [REDACTED]	
 CCI [REDACTED] Viral load in NP swabs and RSV signs and symptoms over time in -participants CCI [REDACTED]

There are no estimands for this study.

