3.4. Other Endpoint(s) (or, Exploratory Endpoints)

3.4.1. Viral Load

Viral load will be measured in NP swabs. Samples will be analyzed to measure RSV A and B RNA levels by reverse transcription polymerase chain reaction (RT-qPCR). For each participant and visit, the numeric viral load value will be the sum of that from subtype A and subtype B, followed by log₁₀ transformation for analysis.

Baseline will be measured pre-dose on Day 1. Change from baseline in viral load will be calculated at each sampled visit.

For viral load summaries, numeric log₁₀ copies/mL values will be derived from the possible categorical results as follows:

PFIZER CONFIDENTIAL

DMB02-GSOP-RF02 8.0 Statistical Analysis Plan Template

TMF Doc ID: 98.03

Page 9 of 20

- If the result is 'TND' (target not detected <LOD), a value of 0 \log_{10} copies/mL will be used, as applicable for both subtype A and B.
- If the result is 'TD' (target detected <LLOQ), the midpoint between the unlogged LLOQ and LOD will be used, ie, a value of 2.91 \log_{10} copies/mL will be used for subtype A (converted from a midpoint of 810 copies/mL) and 2.22 \log_{10} copies/mL for subtype B (converted from a midpoint of 165 copies/mL).
- If the result is '>ULOQ', a value of 9 \log_{10} copies/mL will be used, as applicable for both subtype A and B. Such values may ultimately be replaced by numeric results in subsequent data transfers.

Undetectable RSV viral load is defined as a central PCR laboratory result of 'TND' (or, a converted numeric value of 0 \log_{10} copies/ml) for both subtype A and subtype B.

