5.2. General Methods

The analyses related to the primary and secondary endpoints will be based on the appropriate population for analysis (see Section 4).

Unless otherwise stated, all summaries and plots will be presented by treatment group, by cohort and age band (if data permits), and overall, if applicable. The following treatment group labels (or similar) will be used:

- Placebo
- Sisunatovir

Cohorts and age bands are as follows:

- Cohort 1A: CCI
- Cohort 1B: [REDACTED]
- Cohort 1C: [REDACTED]
- Cohort 1D: [REDACTED]
- Cohort 2A: [REDACTED]
- Cohort 2B: [REDACTED]
- Cohort 2C: [REDACTED]

PFIZER CONFIDENTIAL

DMB02-GSOP-RF02 8.0 Statistical Analysis Plan Template

TMF Doc ID: 98.03

Page 11 of 20

- Cohort 2D: CCI
- Cohort 3E: [REDACTED]
- Cohort 3F: [REDACTED]
- Cohort 3B: [REDACTED]
- Cohort 3D: [REDACTED]

Some measures will be summarized using graphical representations.

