6.4. Other Endpoint(s) (or, Exploratory Endpoint[s])

6.4.1. Viral load

Absolute values and change from baseline in \log_{10} total RSV viral load by RT-qPCR will be summarized descriptively at each sampled visit by treatment, cohort, and age band, as described in Section 5.2.1. No imputation of missing data is planned. The absolute values and change from baseline in \log_{10} total RSV viral load by RT-qPCR at each timepoint will also be listed for each participant.

A spaghetti plot of viral load values over time (by visit) will also be produced, differentiating participants from each treatment group. The number and proportion of participants with TND and TD, RSV viral load at each sampled visit will be presented respectively by treatment, cohort, and age band as described in Section 5.2.2.

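### Children with Day 1 RSV RNA below LLOQ stay in the viral-load change and BLOQ summaries and distort both descriptive estimates

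*SAP*

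**What the plan says.** The tertiary virology endpoint in SAP 2.2 covers "change from baseline at each sampled visit and proportion of participants with BLOQ at Day" (the day is redacted).

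- **Derivation.** SAP 3.4.1 states: "Change from baseline in viral load will be calculated at each sampled visit". Results below the quantification limit receive numbers. For undetected target the rule reads "If the result is 'TND' (target not detected <LOD), a value of 0" log10 copies/mL. Detected but below LLOQ (TD) becomes 2.91 log10 for subtype A, "converted from a midpoint of 810 copies/mL", and 2.22 log10 for subtype B, from a midpoint of 165. The subtypes are summed before the log is taken.
- **Summary.** Under SAP 6.4.1, absolute values and changes "will be summarized descriptively at each sampled visit by treatment, cohort, and age band". TND and TD proportions are given separately by visit. No baseline condition is set and no analysis set is named.
- **Analysis sets.** SAP 5.2 says "The analyses related to the primary and secondary endpoints will be based on the appropriate population for analysis"; it does not mention tertiary endpoints. The Biomarker Analysis Population in SAP 4 needs randomisation, one dose and one reportable parameter (children "in whom at least 1 of the measured parameters of interest can be reported"). The full analysis set needs only the first two.
- **Replacement.** Protocol 4.1 and 9.5 let the Sponsor replace a child "if Day 1 RSV RNA level by RT-qPCR is less than the lower limit of quantification". Neither section removes that child from analysis. The amendment history (Protocol Appendix 11, Amendment 2) gives the reason for this rule as flexibility to replace participants and to evaluate viral-load change over time.
- **Exclusions.** The one stated analysis exclusion, for a discrepant central RSV result (Protocol 4.1), applies to the primary analysis, which is safety. SAP 6.5 plans no subset analysis.

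**The concern.** The replacement rule accepts that a child without quantifiable RNA on Day 1 says little about viral-load change, but the SAP does not carry that through. The replaced child and the replacement both count in the summaries.

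Such children are foreseeable. A local antigen or molecular test is enough for entry (Protocol 5.1), and the baseline RT-qPCR swab is not used for eligibility (Protocol 8.7).

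Two quantities are affected. The mean change mixes declines from a quantified baseline with values produced by the substitution rules. The later BLOQ proportion includes children who were already BLOQ before the first dose. Results are shown by treatment, cohort and age band, so one such child can move a cell noticeably.

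**Working it through.** **Reproducing the plan's own figures.** log10(810) = 2.908, which rounds to 2.91. log10(165) = 2.217, which rounds to 2.22. Both agree with SAP 3.4.1.

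**Formulas.** Let q be the share of a cell that is below LLOQ on Day 1 and d the change those children are assigned. Let mu be the mean change, and p the BLOQ proportion, among the other children.

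- Mean change over all children = (1 - q) x mu + q x d.
- BLOQ proportion over all children = q + (1 - q) x p, if the Day 1 BLOQ children stay BLOQ. The shift from p is therefore q x (1 - p).

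**Values of d under the SAP's substitutions.**

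- TND to TND, or TD to TD: d = 0. A Day 1 TND child is at the floor and cannot decline.
- TD to TND: d is about -2.91 (subtype A) or -2.22 (subtype B). If TND is read literally as 1 copy/mL per subtype before summing, the falls are 2.61 and 1.92.

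A TD-to-TND child therefore dilutes the mean only when the other children fall by more than that amount. Otherwise the child inflates it.

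**Assumptions.** The documents give no q, mu or p, and arm sizes are redacted. Cells of 6 and 4 are illustrative. For scale, the maximum of 108 evaluable children over the 12 cohort and age-band cells in SAP 5.2 averages 108/12 = 9 per cell, both arms together and including repeat enrolment.

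**Mean change with one such child in the cell (log10).**

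| Assumed mu | Cell size | d = 0 | d = -2.91 (A, TD to TND) |
|---|---|---|---|
| -3 | 6 | 5 x (-3)/6 = -2.50 | (-15 - 2.91)/6 = -2.985 |
| -3 | 4 | 3 x (-3)/4 = -2.25 | (-9 - 2.91)/4 = -2.978 |
| -2 | 6 | 5 x (-2)/6 = -1.67 | (-10 - 2.91)/6 = -2.15 |
| -2 | 4 | 3 x (-2)/4 = -1.50 | (-6 - 2.91)/4 = -2.23 |

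At mu = -3, zero change dilutes the mean by 17% or 25%, whereas the TD-to-TND child barely moves it. At mu = -2 the TD-to-TND child makes the decline look larger.

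**Shift in the BLOQ proportion with one child who stays BLOQ, q x (1 - p).**

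| Assumed p | Cell of 6 (q = 1/6) | Cell of 4 (q = 1/4) |
|---|---|---|
| 0% | 16.7 points | 25 points |
| 30% | 11.7 points | 17.5 points |
| 50% | 8.3 points | 12.5 points |

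**The case against.** The strongest reply is that little depends on these tables. The endpoint is tertiary, there are no hypotheses (SAP 5.1), and Protocol 9.3.4 allows such endpoints to be left out of the CSR. The Amendment 3 rationale says viral load is sampled sparsely, with no expectation of detecting a treatment difference. The affected children are also partly visible: SAP 6.4.1 gives TND and TD counts by visit, individual listings and a spaghetti plot, and SAP 6.6.1 counts disagreements between the diagnostic test and the Day 1 swab. In very small cells a careful reader could find the child. All of this stands, and it keeps the point minor. It does not repair the summaries, because no planned table conditions on baseline status.

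Three stronger readings are tempting, and the documents do not support them.

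- A reader might infer that every child below LLOQ on Day 1 can only stay level or rise, so the mean is always diluted. That is true of TND children only. The TD value in SAP 3.4.1 leaves room for an assigned fall of 2 to 3 log10.
- A reader might infer that these children are reported as having cleared the virus. The documents report BLOQ, TND and TD and make no claim of clearance.
- A reader might infer that the Biomarker Analysis Population causes the problem. The SAP never ties that set to viral load. The gap lies in SAP 3.4.1 and 6.4.1.

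**Conclusion.** The point holds as a minor one. As written, children with Day 1 RSV RNA below LLOQ enter both the change-from-baseline and the BLOQ summaries, and replacement does not take them out. The mean change is distorted in a direction that depends on the child's path: diluted if the child stays TND or stays TD, possibly inflated if the child goes from TD to TND. The BLOQ proportion rises by q x (1 - p) for children who stay BLOQ.

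In the illustration, one child moves an assumed mean of -3 to as little as -2.5 or -2.25, or hardly at all. The same child raises the BLOQ proportion by at most 17 or 25 points, and by about 12 or 18 at p = 30%. These sizes rest on assumed cell sizes, mu and p; how often such children occur is not given.

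A reader might go further and infer a biased treatment comparison or an inflated error rate. No between-arm test is planned, so what is affected is how the descriptive tables are interpreted, including any informal comparison of arms.

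**What to change.** In SAP 6.4.1:

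- Present change from baseline and the BLOQ, TND and TD proportions among children whose Day 1 RSV RNA is at or above LLOQ. Say how the two subtypes' limits combine, for example at least one subtype at or above its own LLOQ.
- Count the remaining children by arm and list them with their Day 1 category (TND or TD).
- Keep the all-treated summary as supportive, name the analysis set for each table, and state that replaced children stay in the all-treated version.

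The restriction uses a pre-dose value already collected, so no procedure or safety analysis changes. The cost is a few sentences in the SAP, one extra descriptive table, and slightly fewer children in the restricted one.

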5. GENERAL METHODOLOGY AND CONVENTIONS

Final analysis will be performed after study participant data set release following the last participant last visit.

5.1. Hypotheses and Decision Rules

There are no statistical hypotheses for this study.

5.2. General Methods

The analyses related to the primary and secondary endpoints will be based on the appropriate population for analysis (see Section 4).

Unless otherwise stated, all summaries and plots will be presented by treatment group, by cohort and age band (if data permits), and overall, if applicable. The following treatment group labels (or similar) will be used:

- Placebo
- Sisunatovir

Cohorts and age bands are as follows:

- Cohort 1A: CCI
- Cohort 1B: [REDACTED]
- Cohort 1C: [REDACTED]
- Cohort 1D: [REDACTED]
- Cohort 2A: [REDACTED]
- Cohort 2B: [REDACTED]
- Cohort 2C: [REDACTED]

PFIZER CONFIDENTIAL

DMB02-GSOP-RF02 8.0 Statistical Analysis Plan Template

TMF Doc ID: 98.03

Page 11 of 20

- Cohort 2D: CCI
- Cohort 3E: [REDACTED]
- Cohort 3F: [REDACTED]
- Cohort 3B: [REDACTED]
- Cohort 3D: [REDACTED]

Some measures will be summarized using graphical representations.

5.2.1. Analyses for Continuous Endpoints

For continuous endpoints, the data will be summarized using number of participants, arithmetic mean, standard deviation (SD), median and range (minimum and maximum) in accordance with the sponsor reporting standards. For variables to be analyzed on the natural log scale (\log_e) or base 10 log scale (\log_{10}), the geometric mean and geometric coefficient of variation (%CV) will additionally be calculated.

5.2.2. Analyses for Binary/Categorical Endpoints

For binary or categorical endpoints, number of participants, numbers and percentages of participants meeting the categorical criteria will be presented in accordance with the sponsor reporting standards.

For the endpoints of signs and symptoms, a shift table of number of participants with and without a sign/symptom at Day [REDACTED] against baseline will be summarized for each sign/symptom separately. The proportion of participants with signs and symptoms will also be reported and plotted over time.

5.3. Methods to Manage Missing Data

For the analysis of safety endpoints, the sponsor data standard rules for imputation will be applied.

In all PK data presentations (except listings), concentrations below the limit of quantification (BLOQ) will be set to zero.

In listings, BLOQ values (for PK or PD) will be reported as "<LLOQ", where LLOQ will be replaced with the value for the LLOQ.

In listings of viral load, BLOD values will be reported as "TND" and BLOQ values will be reported as "TD".

For PK and PD summary tables and plots of median profiles, statistics will be calculated having set concentrations to missing if one of the following cases is true:

1. A concentration has been collected as ND (i.e., not done) or NS (i.e., no sample)
2. A deviation in sampling time is of sufficient concern or a concentration has been flagged anomalous by the pharmacokineticist/statistician.

6. ANALYSES AND SUMMARIES

6.1. Primary Endpoint(s)

All analyses of primary endpoints (safety analyses) will be performed on the safety population defined in Section 4.

6.1.1. Incidence of TEAEs

The incidence of TEAEs will be tabulated by cohort, age band and treatment.

6.1.2. Incidence of AEs and SAEs leading to discontinuations

The incidence of AEs and SAEs leading to discontinuation will be tabulated by cohort, age band and treatment. The safety analysis set will be used.

6.1.3. Incidence of clinically significant abnormal laboratory values, and vital signs.

Any clinical laboratory and vital signs abnormalities of potential clinical concern will be described. Safety data will be presented in tabular and/or graphical format and summarized descriptively, where appropriate.

6.1.3.1. Laboratory values

Safety laboratory data will be listed and summarized by treatment group, cohort and age band and overall, in accordance with the sponsor reporting standards using the safety analysis set defined in Section 4. Baseline is as defined in Section 3.1.3.1. Data collected at screening that are used for inclusion/exclusion criteria, will be considered source data, and will not be required to be reported, unless otherwise noted.

6.1.3.2. Vital Signs

Absolute values and CFB in systolic and diastolic BP, pulse rate, temperature respiratory rate, and SpO₂ will be listed and summarized by cohort, age band, treatment and timepoint, according to sponsor reporting standards, using the safety analysis set defined in Section 4. Baseline is as defined in Section 3.1.3.2.

Mean absolute values and CFB for systolic and diastolic BP, pulse rate, temperature, respiratory rate, and SpO₂ will be plotted against time point. On each plot there will be one line for each cohort and age band with all treatments on the same plot. Corresponding individual plots of changes from baseline will also be produced for each treatment.

Maximum increase and decrease from baseline over all measurements taken post-dose for systolic and diastolic BPs, pulse rate, temperature respiratory rate, and SpO₂ will be summarized by cohort, age band and treatment, according to sponsor reporting standards.

6.2. Secondary Endpoint(s)

6.2.1. Pharmacokinetic analysis

The plasma concentrations of sisunatovir will be listed and descriptively summarized by nominal PK sampling time, treatment, age group, and cohort. Individual participant and summary profiles (mean and median plots) of the plasma concentrations data will be plotted

by treatment, cohort and age group using actual and nominal times, respectively. Mean and median profiles will be presented on both linear and semi-log scales.

Nominal time recorded as 2H post dose corresponds to [CC1] post dose and nominal time recorded as 6H post dose corresponds to [CC1] post dose. When nominal time is [CC1] post dose, 54 min – 132 min is within 10% nominal time. When nominal time is [CC1] post dose, 216 min – 396 min is within 10% nominal time. The following will be presented for the plasma concentration data using the PK Concentration Set if data permits (as defined in Section 4):

- For each cohort and age band, a listing of all concentrations sorted by participant ID and nominal time post-dose. The concentration listing will also include the actual times. Deviations from the nominal time will be given in a separate listing.
- For each cohort and age band, a summary of concentrations by each nominal time post-dose, where the set of statistics will include n, mean, median, standard deviation, coefficient of variation (cv), minimum, maximum and the number of concentrations above the lower limit of quantification.
- median concentration time plots (on both linear and semi-log scales) against nominal time post-dose. One plot for each scale will be presented, which will include all cohorts and age bands in the same plot.
- individual concentration time plots by cohort and age band (on both linear and semi-log scales) against actual time post-dose (there will be separate spaghetti plots for each cohort and age band, with a line for each participant per scale).
- individual concentration time plots by participant (on both linear and semi-log scales) against actual time post-dose.

The nominal PK sampling time will be used for summary statistics and relevant median plots, whereas for individual participant plots by time, the actual PK sampling time will be used.

The final population PK model will be used to simulate plasma concentration-time curves for sisunatovir for individuals and to calculate post-hoc estimates of PK parameters (CL/F, C_{max}, C_{min}, AUC and t_{1/2}) by age group.

Data permitting, geometric means of PK parameters estimated from the final population PK model will be summarized descriptively by treatment and age group. A stand-alone population PK modeling and simulation analysis plan will be prepared, and the results will be reported in a stand-alone report, outside of the clinical study report.

